**Table 41: Summary of Non-fatal Overdoses by Treatment Arm**

		Treatment Arm		
Visit		TAU (N=XX)	PILOT (N=XX)	Total (N=XX)
	Min			
	25 th Percentile			
	Median			
	75 th Percentile			
	Max			
	Number of participants with at least one opioid overdose since last study visit			
	Number of overdoses with additional information during this assessment period 			
	NARCAN (naloxone) used to reverse overdose 			
	Don't know			
	No			
	Yes			
	Overdose resulting in treatment at an Emergency Department 			
	No			
	Yes			
	Overdose resulting in being admitted to the hospital 			
	No			
	Yes			

Overdoses as captured on the Overdose Information (ODI) form.

 Number of overdoses out of the up to two most recent overdoses collected per participant per visit.

 Percentage is based on the denominator of number of opioid overdoses.

Listing 3: Non-Fatal Overdoses by Treatment Arm											
Treatment Arm = TAU							Most Recent Overdoses 				
Site	Participant ID	Date of Randomization	Date of Assessment	Visit	Number of Overdoses 	Overdose Involving Opioids	Required NARCAN (naloxone) to Reverse Overdose	Required Treatment at an Emergency Department	Required Being Admitted to the Hospital	Substances Used	Participant was Trying to Overdose
xxxxx	xxxxxxxxxxxx	mm/dd/yyyy	mm/dd/yyyy	Baseline/ Day 30/ Day 90/ Day 180/ Day 210	N	No/Yes	N	N	N	Opioids/ Benzodiazepines/ Cocaine/ Methamphetamine/ Alcohol/ Barbiturates/ Other: {specify}	No/ Yes

Overdoses as captured on the Overdose Information (ODI) form. All visits with ODI completed are included for participants who reported at least one overdose (excluding index overdose) at any visit.

 At baseline, number of overdoses in the past 30 days. At Day 30, Day 90, Day 180 and Day 210 visits, number of overdoses since last study visit.

 Number of overdoses out of the up to two most recent overdoses collected per participant per visit.

Listing 3: Non-Fatal Overdoses by Treatment Arm											
Treatment Arm = PILOT							Most Recent Overdoses 				
Site	Participant ID	Date of Randomization	Date of Assessment	Visit	Number of Overdoses 	Overdose Involving Opioids	Required NARCAN (naloxone) to Reverse Overdose	Required Treatment at an Emergency Department	Required Being Admitted to the Hospital	Substances Used	Participant was Trying to Overdose
xxxxx	xxxxxxxxxxxx	mm/dd/yyyy	mm/dd/yyyy	Baseline/ Day 30/ Day 90/ Day 180/ Day 210	N	No/Yes	N	N	N	Opioids/ Benzodiazepines/ Cocaine/ Methamphetamine/ Alcohol/ Barbiturates/ Other: [specify]	No/ Yes

Overdoses as captured on the Overdose Information (ODI) form. All visits with ODI completed are included for participants who reported at least one overdose (excluding index overdose) at any visit.

 At baseline, number of overdoses in the past 30 days. At Day 30, Day 90, Day 180 and Day 210 visits, number of overdoses since last study visit.

 Number of overdoses out of the up to two most recent overdoses collected per participant per visit.

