2.5 Safety Reporting

Given the low-risk nature of the PILOT intervention, only targeted Safety Event reporting will be conducted during this study. Specifically, deaths, post-index visit overdoses, suicidal ideation, Emergency Department (ED) visits, and hospitalizations will be solicited during the 30-, 90-, 180-, and 210-day visits (or in-between visits if reported spontaneously). Reporting timeframes for these targeted Safety Events will follow regulatory requirements. While active suicidal ideation at the

screening/baseline visit is considered an exclusion criterion, participant suicidal ideation occurring after enrollment will be addressed in accordance with **Section 11.7.1**.

For the purposes of this protocol, the following events do not require reporting in the data system:

- Pregnancy
- Admission for detoxification
- Elective hospitalization

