11.4.2 Visit Documentation

This form documents visit attendance, non-visit attendance, and missed visits. This form additionally captures whether any ED visits or hospitalizations occurred since the last study visit, and if so, it triggers the ED Visit and Hospitalization form. This assessment has been recently developed to document visits that could occur out of window, off site, or missed due to COVID-19. This is a visit-based form expected at all visits that would typically have a regular missed visit form. If a visit is missed for any reason, this form will capture the reason a study visit was missed. Completing this form and indicating that the visit was not attended will remove the requirement

for all assessments scheduled for that visit. Active tracking and follow-up should be performed for all missed visits. The form also captures specific data collection settings if applicable (such as in clinic, off-site, remote, or in a controlled environment).

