11.4.12 ED Visits and Hospitalizations

Data will be collected on health care utilization (inpatient and outpatient) between the index and 30-, 90-, 180-, and 210-day assessments and on an as needed basis for spontaneous reporting that occurs between study visits. ED visits and hospitalizations will be collected through self-report and review of participant electronic medical records.

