## 7.7 Definition of the Exploratory Outcome Measures

1. Exploratory Aim 1: To assess the effects of PILOT versus TAU on the achievement (yes/no) and magnitude of achievement (e.g., improvement in Addiction Recovery Capital Scale by 3 points, number of steps achieved) on the modified SUD Cascade of Care.
2. Exploratory Aim 2: To evaluate the effectiveness of PILOT versus TAU on initiation of MOUD in the ED (EDM) for those with any level of OUD at baseline (DSM; assessed via self-report upon ED discharge or in follow-up assessment if unable to be assessed at ED discharge).
3. Exploratory Aim 3: To assess the effects of PILOT versus TAU on substance use frequency at 30, 90, and 180 days via self-reported days of illicit opioid use measured by Timeline Follow-Back (TLFB).
4. Exploratory Aim 4: To evaluate the degree of engagement in Peer Support Services in those randomized to PILOT versus TAU at 30, 90, and 180 days, measured as the number of contacts received or initiated with a Peer Support Specialist in the past month (PIL; phone, video, or in-person).

5. Exploratory Aim 5: To evaluate the effectiveness of PILOT versus TAU on self-reported attendance in 12-step meetings, peer support services, other recognized recovery organization, or formal SUD treatment at any time point during enrollment, defined as self-report of having attended a meeting or appointment (SAA; phone, video, or in-person).
6. Exploratory Aim 6: To evaluate the effectiveness of PILOT versus TAU on the percentage of urine toxicology screens (UDT) positive for primary substance of use (as per DSM-5 Checklist: opioids, alcohol, amphetamines, cannabis, cocaine, or sedatives) at 30-, 90-, 180-, and 210-days post-randomization.
7. Exploratory Aim 7: To evaluate the effectiveness of PILOT versus TAU on repeat non-fatal overdose (ODI) and 210-day rates of death (DTH; all-cause mortality), including death by overdose.

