### **8.3 Overdoses**

A summary table will be provided with the number of non-fatal opioid overdoses by treatment arm and by study visit (Baseline, Day 30, Day 90, Day 180, and Day 210 follow-up visit) as captured on the Overdose Information (ODI) form. At the baseline visit, participants are asked about overdoses in the past 30 days. At Day 30, Day 90, Day 180, and Day 210 follow-up visits, participants are asked about overdoses since the last study visit. The number of overdoses where NARCAN (naloxone) was used to reverse overdose, overdoses that resulted in treatment at an ED, and overdoses that resulted in being admitted to the hospital will also be summarized by treatment arm, of the two most recent overdoses per participant per visit. The number of participants with at least one opioid overdose and the number of opioid overdoses per participant (including participants experiencing no opioid overdoses) will also be summarized by treatment arm. A detailed listing of non-fatal opioid overdoses by treatment arm will be provided. The listing will include Site, Participant ID, date of enrollment, visit, date of assessment, number of overdoses, and comments from the Overdose Information (ODI) form.

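### Repeat non-fatal overdose is counted only from the visit-based ODI form, so an overdose recorded only on the EDH form is missing from the overdose table and from Exploratory Aim 7

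*SAP*

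**What the plan says.** **Where the overdose count comes from.** SAP 8.3 summarizes non-fatal opioid overdoses by visit "as captured on the Overdose Information (ODI) form". Table 41 carries the footnote "Overdoses as captured on the Overdose Information (ODI) form". Listing 3 has the same source and shows only visits at which ODI was completed. SAP 7.7 defines Aim 7 as the effect of PILOT versus TAU "on repeat non-fatal overdose (ODI) and 210-day rates of death (DTH; all-cause mortality), including death by overdose". EDH is named in none of these places.

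**When ODI is completed.** Protocol Table 1 (section 11.2) schedules ODI at baseline and Days 30, 90, 180 and 210, with no as-needed mark. After baseline, "participants are asked about overdoses since the last study visit" (SAP 8.3). On a missed visit, Protocol 11.4.2 says of the Visit Documentation form: "Completing this form and indicating that the visit was not attended will remove the requirement" for the assessments due at that visit.

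**What EDH holds.** EDH is marked as needed in Table 1. Protocol 11.4.12 states that "ED visits and hospitalizations will be collected through self-report and review of participant electronic medical records", and it allows entries for spontaneous reports between visits. SAP Tables 39 and 40 show, by arm, participants whose hospitalization or ED visit is coded *Related to overdose*, taken from EDH.

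**What the plan intends.** Protocol 2.5 makes post-index overdose a targeted safety event, solicited at visits "or in-between visits if reported spontaneously". SAP 7.8 item 7 analyses a non-fatal overdose occurring at any point in study participation. It uses an odds ratio and a chi-squared test, with time-to-event methods as an option if dropout is likely. SAP 7.9 plans no missing-data method for exploratory outcomes.

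**The concern.** The database can hold a known overdose that the overdose count never uses. The form that feeds the count depends on attendance. The form that can be filled without attendance does not feed the count.

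Repeat overdose is a targeted safety event. It is also one of the Milestone 3 markers (Protocol 7.4) meant to help size a larger trial, so an undercount would carry into that planning. If attendance differs between arms, the Aim 7 comparison could also be distorted. That is plausible here, because PILOT peers attempt contact at least weekly (SAP 6.2) and TAU has no equivalent.

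**Working it through.** The documents give no repeat-overdose rate, attendance rate or power figure for this outcome, so there is no plan figure to reproduce. The check is a trace of sources, followed by an illustration on assumed inputs.

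**Trace.** Take a participant who attends Day 30, is treated in the ED for an overdose on Day 70 that is entered on EDH (from records or a spontaneous report), and attends nothing afterwards.

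- Table 40: appears in the overdose-related row for the treatment period.
- Table 41 and Listing 3: no ODI exists after Day 30, so the Day 70 overdose is absent.
- Aim 7, binary version: no ODI event. The SAP does not say whether the person counts as event-free or leaves the denominator. The overdose is lost either way.
- Aim 7, time-to-event version: the person is censored and the event is not added.

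A participant who misses Day 90 but attends Day 180 can still report the event, because ODI asks about the time since the last visit. The loss therefore falls mainly on people who stop attending.

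**Illustration.** About 150 participants randomized 1:1 (SAP 2.2.1) gives 75 per arm. Assumptions not in the documents: the same true risk *r* in both arms; a share *a* of participants with an overdose whose event is visible on ODI; and a share *c* of the missed cases that EDH recovers. Anyone without a visible event is counted as event-free.

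Observed risk = r × [a + (1 − a) × c]. OR = odds in PILOT ÷ odds in TAU.

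With r = 0.30, a = 0.80 in PILOT and 0.65 in TAU:

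| EDH recovery (PILOT / TAU) | Observed risk PILOT | Observed risk TAU | OR (true value 1) |
|---|---|---|---|
| None (ODI only) | 0.30 × 0.80 = 0.240 | 0.30 × 0.65 = 0.195 | (0.240/0.760) ÷ (0.195/0.805) = 1.30 |
| 0.3 / 0.3 | 0.30 × 0.86 = 0.258 | 0.30 × 0.755 = 0.2265 | 1.19 |
| 0.5 / 0.5 | 0.30 × 0.90 = 0.270 | 0.30 × 0.825 = 0.2475 | 1.12 |
| 0.7 / 0.7 | 0.30 × 0.94 = 0.282 | 0.30 × 0.895 = 0.2685 | 1.07 |
| 0.7 / 0.3 | 0.282 | 0.2265 | (0.282/0.718) ÷ (0.2265/0.7735) = 1.34 |

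Participants with an overdose missed under ODI only: 75 × 0.30 × 0.20 + 75 × 0.30 × 0.35 = 4.5 + 7.9 = 12.4, out of 2 × 75 × 0.30 = 45.

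Range for ODI only:

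- r = 0.20, shares 0.80/0.70: (0.16/0.84) ÷ (0.14/0.86) = 1.17.
- r = 0.40, shares 0.90/0.70: (0.36/0.64) ÷ (0.28/0.72) = 1.45.

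If the 0.80 and 0.65 are swapped between arms, the OR becomes 1/1.30 = 0.77. The direction depends wholly on which arm is better observed.

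**The case against.** **The events are not lost from the report.** This stands. Overdose-related ED visits and hospitalizations appear by arm in Tables 39 and 40, each footnoted to its form. A difference between Tables 40 and 41 is not in itself a contradiction, because they measure different things. What is missing is the event in the overdose count and in Aim 7.

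**Self-report looks deliberate.** Milestone 3 speaks of self-reported overdoses. That explains ODI as the main source and is a reason to keep that count. It does not explain leaving known events out of an analysis meant to cover any time in the study.

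**The plan allows for dropout.** SAP 7.8 item 7 offers Kaplan-Meier, log-rank, Cox and Fine-Gray methods. The odds ratios above apply only to the naive binary version. The provision is optional, though, and adds no EDH events.

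**A reader might infer that the plan makes PILOT look harmful, with a false OR near 1.3.** The documents do not support that. The visible shares are assumed, and no rule says that non-attenders count as event-free. Visibility is also not attendance: an overdose reported before someone stops coming is counted. Protocol 4.1 puts the highest risk of death in the first month, which Day 30 covers, so visible shares may well exceed late attendance.

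**Adding EDH could worsen the imbalance.** This stands. EDH also takes spontaneous reports, and weekly peer contact could produce more of them in PILOT. The last row of the table shows the effect.

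**Simple pooling would admit the wrong events.** This stands too. The EDH listings allow a fatal outcome, and the overdose rows in Tables 39 and 40 do not specify opioids. ODI detail covers only the two most recent overdoses per visit, so full date matching may be impossible.

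**A reader might take record review after loss to follow-up as already planned.** Protocol 11.4.12 does not say so. The number of recoverable events is unknown.

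**Conclusion.** The gap in sources is real and does not depend on any assumed number. As written, an overdose known only from EDH is absent from SAP 8.3, Table 41, Listing 3 and Aim 7, mainly for participants who stop attending. The time-to-event option does not restore it.

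The size and direction of any bias between arms are unknown. The 1.30 rests on an assumed 30% risk, assumed visibility of 80% versus 65%, and the naive binary analysis. With EDH added, the same assumptions give 1.19 to 1.07 under equal recovery and 1.34 under recovery that favours PILOT. These figures show sensitivity; they do not predict a result.

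The outcome is a safety and exploratory one, and SAP 7.8 allows exploratory methods to change. The primary and secondary analyses and the sample size are untouched. The change is still worth making, because it concerns a targeted safety event and the plan already collects the data.

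**What to change.** Keep the ODI-only count. In SAP 8.3 and Table 41, and in SAP 7.8 item 7, add a second count and specify:

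1. **Definition.** A participant counts (yes/no) if a post-randomization non-fatal overdose is on ODI or on an EDH entry marked *Related to overdose*. Counting people rather than events removes the need for full date matching.
2. **Exclusions.** Leave out EDH entries with a fatal outcome, and any admission that continues from the index ED visit. Table 40 excludes the index visit, but the Table 39 footnotes are silent. Report opioid involvement separately where it is known.
3. **Time-to-event version.** Use EDH events there as well.
4. **Source.** Show for each event whether it came from ODI, EDH or both. Repeat the comparison without events known only from spontaneous between-visit reports.
5. **Record review.** Apply the same review period to both arms, within each participant's consent and authorization.

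The cost is SAP wording, a few table rows and a source column. Two items may take more. The EDH listings show no field for how an entry became known, so one may be needed for item 4. A uniform review period may also add site work. The combined count mixes self-report with records and recovers only overdoses that led to ED or hospital care, which is why the ODI-only count should stay beside it.

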**Table 42: Summary of Suicide Risk by Treatment Arm**

		Treatment Arm		
Visit	Over the last two weeks, how often have you been bothered by thoughts that you would be better off dead, or of hurting yourself in some way? 	TAU (N=XX)	PILOT (N=XX)	Total (N=XX)
Screening	Responses 			
	Not at all			
	Several days			
	More than half the days			
	Nearly every day			
Day 30	Responses 			
	Not at all			
	Several days			
	More than half the days			
	Nearly every day			
Day 90	Responses 			
	Not at all			
	Several days			
	More than half the days			
	Nearly every day			
Day 180	Responses 			
	Not at all			
	Several days			
	More than half the days			
	Nearly every day			
Day 210	Responses 			
	Not at all			
	Several days			
	More than half the days			
	Nearly every day			

 This question is asked as part of the 9-item version of the Patient Health Questionnaire (PHQ-9).

 The percentage of the number of responses is calculated with the number randomized as the denominator. The percentage for individual responses is calculated with the number of responses as the denominator.

Listing 4: Suicide Risk by Treatment Arm					
Treatment Arm = TAU					
Site	Participant ID	Date of Randomization	Date of Assessment	Visit	Thoughts You are Better Off Dead or of Hurting Yourself
xxxxx	xxxxxxxxxxxx	mm/dd/yyyy	mm/dd/yyyy	Screening/ Day 30/ Day 90/ Day 180/ Day 210	Not at all/ Several days/ More than half the days/ Nearly every day

All visits with PHQ-9 completed are included for participants who indicate suicide risk at any visit. For PHQ-9 suicide risk is indicated by a response of "Several days", "More than half the days" or "Nearly every day".

Listing 4: Suicide Risk by Treatment Arm					
Treatment Arm = PILOT					
Site	Participant ID	Date of Randomization	Date of Assessment	Visit	Thoughts You are Better Off Dead or of Hurting Yourself
xxxxx	xxxxxxxxxxxx	mm/dd/yyyy	mm/dd/yyyy	Screening/ Day 30/ Day 90/ Day 180/ Day 210	Not at all/ Several days/ More than half the days/ Nearly every day

All visits with PHQ-9 completed are included for participants who indicate suicide risk at any visit. For PHQ-9 suicide risk is indicated by a response of "Several days", "More than half the days" or "Nearly every day".

**Listing 5: Deaths by Treatment Arm**

**Treatment Arm = TAU**

Site	Participant ID	Date of Randomization	Date of Death	Source of Death Report	Type	Cause of Death	MedDRA V26.1		Contributing Factors
							Preferred Term	System Organ Class	
xxxxx	xxxxxxxxxxxx	mm/dd/yyyy	mm/dd/yyyy	Medical chart/ Death certificate/ Autopsy report/ Treating physician/ Other	Primary/ Secondary	xxxxxxxxxxxx xxxxxxxxxxxx	xxxxxxxxxxxx xxxxxxxxxxxx	xxxxxxxxxxxxxxxxxxxx xxx	Alcohol/Drug/ None/ Unknown

Listing 5: Deaths by Treatment Arm									
Treatment Arm = PILOT									
Site	Participant ID	Date of Randomization	Date of Death	Source of Death Report	Type	Cause of Death	MedDRA V26.1		Contributing Factors
							Preferred Term	System Organ Class	
xxxxx	xxxxxxxxxxxx	mm/dd/yyyy	mm/dd/yyyy	Medical chart/ Death certificate/ Autopsy report/ Treating physician/ Other	Primary/ Secondary	xxxxxxxxxxxxxx xxxxxxxxxxxxxx	xxxxxxxxxxxxxx xxxxxxxxxxxxxx	xxxxxxxxxxxxxxxxxxxx xxx	Alcohol/Drug/ None/ Unknown

### 17.1.9 Data Quality

Table 43: Summary of Data Audits				
Site	Date of Audit	Total Fields Audited	Total Data Discrepancies	Error Rate
Site 1	mm/dd/yyyy	N	N	X.XX%
	Subtotal			
Site 2	mm/dd/yyyy			
	Subtotal			
Site 3	mm/dd/yyyy			
	Subtotal			
Total				

 Fields reviewed at monitoring visit comparing the database to source documentation.

 Fields discrepant between database and source documentation.

### 17.1.10 Protocol Deviations

Table 44: Summary of Protocol Deviations				
	Site 1	Site 2	Site 3	Total
Total number of protocol deviations	N			
Number of participants impacted per protocol deviation				
None	N (X%)			
One				
More than one				
Total number of major protocol deviations	N			
Type of major protocol deviation				
No consent/assent obtained	N (X%)			
Unauthorized assessments and/or procedures conducted prior to obtaining informed consent/assent				
Non-IRB approved/outdated/obsolete informed consent/assent documents				
Ineligible participant randomized/inclusion/exclusion criteria not met or eligibility not fully assessed prior to randomization				
Study assessments/procedures not followed in accordance with the study protocol				
Stratification error				
Study behavioral intervention was not provided/performed as per protocol				
Safety event not reported				
Safety event reported out of protocol specified reporting timeframe				
Safety event not elicited, observed and/or documented as per protocol				
Safety event assessment not conducted per protocol				
Destruction of study materials without prior authorization from sponsor				

**Table 44: Summary of Protocol Deviations**

	Site 1	Site 2	Site 3	Total
Breach of Confidentiality				
Other informed consent/assent procedures issues				
Other inclusion/exclusion criteria issues				
Other laboratory assessments issues				
Other study procedures/assessments issues				
Other randomization procedures issues				
Other study behavioral intervention issues				
Other safety event issues				
Other significant deviations issues				
Total number of minor protocol deviations	N			
Type of minor protocol deviation				
No consent/assent obtained	N (X%)			
Unauthorized assessments and/or procedures conducted prior to obtaining informed consent/assent				
Non-IRB approved/outdated/obsolete informed consent/assent documents used				
Ineligible participant randomized/inclusion/exclusion criteria not met or eligibility not fully assessed prior to randomization				
Study assessments/procedures not followed in accordance with the study protocol				
Stratification error				
Study behavioral intervention was not provided/performed as per protocol				
Safety event not reported				
Safety event reported out of protocol specified reporting timeframe				
Safety event not elicited, observed and/or documented as per protocol				

**Table 44: Summary of Protocol Deviations**

	Site 1	Site 2	Site 3	Total
Safety event assessment not conducted per protocol				
Destruction of study materials without prior authorization from sponsor				
Breach of Confidentiality				
Other inclusion/exclusion criteria issues				
Other laboratory assessments issues				
Other study procedures/assessments issues				
Other randomization procedures issues				
Other study behavioral intervention issues				
Other safety event issues				
Other significant deviations issues				

